6.1.2 Medical history	
6.1.3 Disease history	
6.1.4 Medication history	13
6.1.4 Medication history6.2 Efficacy	13 13
 6.1.4 Medication history 6.2 Efficacy 6.2.1 Additional analyses 	13 13 14
 6.1.4 Medication history	13 13 14 14
 6.1.4 Medication history	13 13 14 14 14
 6.1.4 Medication history 6.2 Efficacy 6.2.1 Additional analyses 6.2.2 Subgroup analysis 6.3 Pharmacokinetics/pharmacodynamics 6.4 Safety 	13 13 14 14 16 16
 6.1.4 Medication history	13 13 14 14 16 16 16
 6.1.4 Medication history	13 13 14 14 16 16 16 16
 6.1.4 Medication history	13 13 14 14 16 16 16 16 17
 6.1.4 Medication history	13 13 14 14 16 16 16 16 16 17 17
 6.1.4 Medication history	13 13 14 14 16 16 16 16 16 17 17
 6.1.4 Medication history	13 13 14 14 16 16 16 16 17 17 17 17
 6.1.4 Medication history	13 13 14 14 16 16 16 16 16 17 17 17 17 17
 6.1.4 Medication history	13 13 14 14 16 16 16 16 16 17 17 17 17 17 17

Page: 3 of 19:

Abbreviations

AE	Adverse event
AESI	Adverse event of special interest
BMI	Body Mass Index
CRF	Case report form
CSR	Clinical Study Report
DMC	Data Monitoring Committee
eCRF	Electronic case report form
ED	Exposure Day
EPD	Electronic Patient Diary
EU	European Union
FVIII	Factor VIII
HEOR	Health Economics, Outcomes & Reimbursement
ISR	Infusion site reaction
ITI	Immune tolerance induction
ITT	(modified) intent to treat set
IU	International Unit
IV	Intravenous
LOS	Listing only set
MedDRA	Medical dictionary for regulatory activities
MTP	Minimally Treated Patient
OD	On demand
PD	Pharmacodynamics
РК	Pharmacokinetics
PPS	Per protocol set
PUP(s)	Previously Untreated Patient(s)
SAE	Serious adverse event
SAF	Safety (set)
SAP	Statistical analysis plan
SC	Subcutaneous
SD	Standard deviation
TLF	Tables, Listings, Figures
US	United States (of America)

1. Introduction

This statistical analysis plan (SAP) for study 13400 is based on the Integrated Protocol that integrates the original protocol and these following global amendments:

Original protocol, Version 1.4, 20 Sep 2010 Amendment 1 forming integrated protocol Version 2.0, 31 Mar 2011 Amendment 3 forming integrated protocol Version 3.0, 03 Sep 2012 Amendment 4 forming integrated protocol Version 4.0, 08 Apr 2014 Amendment 6 forming integrated protocol Version 5.0, 19 Feb 2016 Amendment 7 forming integrated protocol Version 6.0, 30 May 2017 Amendment 8 forming integrated protocol Version 7.0, 01 Feb 2019 (Amendment 2 and Amendment 5 are local amendments.)

Background

Hemophilia A is a genetic bleeding disorders caused by the deficiency of Factor VIII (FVIII). Persons with mild hemophilia (6% – 49% Factor level) may have excessive bleeding following dental procedures, injury or surgery, while moderate (1% to 5% factor activity) and severe (< 1% factor activity) hemophilia are typically characterized by more frequent and severe bleeding complications. Persons with severe hemophilia may experience not only bleeding after injury, trauma or surgery, but also spontaneous bleeding into joints, muscles and internal organs, including the brain. Recurrent bleeding into joints results in chronic debilitation.

The standard treatment for hemophilia A is replacement therapy, with intravenous (IV) administration of plasma-derived or recombinant FVIII. Some subjects treat bleeding episodes as they occur (i.e., on-demand [OD] treatment), while others treat themselves prophylactically to prevent bleeding according to the recommendations from the World Health Organization. In recent years, prophylactic treatment has become the prevailing type of hemophilia treatment in most developed countries.

The proven clinical benefits of prophylaxis have led to a shift in treatment paradigm from OD treatment to the use of prophylaxis in many countries.

Effective treatment options are significantly lower if inhibitory antibodies against the FVIII (inhibitors) develop. The inhibitors interfere with the infused factor concentrates rendering them ineffective and requiring the use of high dosed FVIII (Imune Tolerance Induction [ITI]) or costly and less effective alternative hemostatic agents, defined as "bypassing agents". The incidence of new FVIII inhibitors in subjects with severe FVIII deficiency is up to half of the patients. Inhibitor development is currently the most significant treatment complication seen in subjects with hemophilia. While improvements in hemostatic agents for subjects with significant morbidity, including a higher rate of bleeding complications, increased disability, and a decreased quality of life.

This SAP describes the objective, study design, analysis sets, all endpoints, and statistical analysis methods for the interim analysis of the part B of study 13400, where Previously Untreated Patients (PUPs) and Minimally Treated Patients (MTPS) where treated. Planned end was 50 exposure days (EDs), in case of inhibitor development the subjects should leave the study and get treatment in the extension part or outside of the study. Complete details of Tables, Listing and Figures (TLFs) specifications as well as dataset details and data handling

specifications will be provided in "TLF specifications" and "Analysis Datasets" documents which are an integral part of this SAP.

The analysis of the 6-month data for Previously Treated Patients (PTPs) in Part A is complete and reported in the clinical study report A51496. This SAP is applicable to completion of Part B. The extension study is ongoing.

The data upon completion of Part B will be analyzed later. The overall study will be closed after all subjects in Parts A and B have completed their respective extensions, in accordance with the protocol definition of 'end of study' (that is, last visit of the last subject [including subjects in the extension study]).

Further details can be found in the Clinical study protocol, which contains comprehensive information on the study drug.

2. Study Objectives

General objectives of this study are:

Primary objective

• To demonstrate the safety and efficacy of treatment with BAY 81-8973 for prophylaxis and breakthrough bleeds in children with severe hemophilia A

Secondary objectives

- To assess the safety and efficacy of BAY 81-8973 during surgeries
- To assess incremental recovery of BAY 81-8973
- To characterize pharmacokinetics in a subset of children

As during part B of this study, where PUPs and MTPs were treated up to 50 EDs (or development of inhibitor) only few recovery and pharmacokinetic data were collected, the last two secondary objectives will be analyzed in the final analyses of the study where more data are available.

3. Study Design

From the protocol:

This is a phase-III multicenter, open-label uncontrolled study to demonstrate safety and efficacy of treatment with BAY 81-8973 for prophylaxis, breakthrough bleeds, and surgeries in children with severe hemophilia A. The study will be conducted worldwide.

The study is divided into two parts: Part A will investigate a total of 50 PTPs up to 12 years of age. Part B will include at least 25 PUPs, plus up to additional 25 PUPs/MTPs (as of Amd 6). All subjects will receive prophylactic administration of BAY 81-8973. Subjects in Part A will be treated with 25-50 IU/kg at least 2 times per week, or more frequently as needed for prophylaxis.

Treatment in Part B may begin with start of prophylaxis with 15-50 IU/kg (minimum dose 250 IU) at least one day a week, or with the subject's first bleeding event. The study drug will be used both for treatment of bleeding events and prevention of bleeds and with surgical procedures. Individual subject dose decisions are at the discretion of the investigator (as of Amds 1 and 3).

Statistical Analysis Plan PH-41074

Protocol No.: BAY 81-8973 / 13400

Page: 6 of 19:

Enrollment will be staggered. Part A will start after 20 adult/adolescent subjects have received 50 ED with BAY 81-8973 without safety concerns in previous studies with BAY 81-8973. PTPs age 6 to 12 years will begin enrollment first, followed by PTPs <6 years (as of Amd 3). Part B, for PUPs/MTPs (as of Amd 6) will begin enrollment after 20 children in Part A have had 50 ED. As of Amd 7, enrollment in Part B will be staggered. 10 patients will be enrolled, and will commence treatment for 20 ED. While safety assessment of the first cohort is ongoing, screening for the next sequence of 10 patients will continue. Treatment of next sequence/10 patients will start if no safety concerns are identified in the previous cohort following completion of 20 EDs. In the event patients would require FVIII treatment, they could still be eligible according to protocol definitions in case no more than 3 EDs of an alternative FVIII product has been administered.

Enrollment will be suspended if the inhibitor rate in the first cohort exceeds 50% following discussion with an independent Data Monitoring Committee (DMC) (as of Amd 7). The total study duration (including screening period) per subject in Part A (as of Amd 1) will be approximately 6-8 months (as of Amd 1) during which the subjects will accumulate at least 50 ED. For Part B, subjects will continue in the study until achieving 50 ED.

Consequently the duration will vary depending upon the frequency of prophylactic infusion and number of bleeding events. All subjects in both Parts A and B (as of Amd 1) will be offered participation in an open label extension study for an additional 6-12 months to allow observations for (as of Amd 1) at least 100 ED. In countries where BAY 81-8973 is marketed under the proprietary name Kovaltry, the option to transition to marketed drug after completion of part B (50EDs) is possible. Enrollment of PUPs/MTPs (as of Amd 6) in Part B and the extension study may continue after Part A and the extension study for PTPs have been completed (as of Amd 1).

During the study, all subjects will receive treatment only with BAY 81-8973 for prophylaxis and treatment of bleeds. In Part A, the (as of Amd 1) dosage range for prophylaxis treatment will be 25-50 IU/kg administered at least 2 times per week at the investigator's discretion. In Part B, PUPs/MTPs (as of Amd 6) may start at a lower dose at (as of Amd 1) once per week schedule at the investigator's discretion. (as of Amd 1) The dosing for breakthrough bleeds will be dependent upon the bleeding location and severity, and will be consistent with local (as of Amd 1) standards of care. Bleeding and treatment (as of Amd 1) information will be collected using an electronic patient (as of Amd 1) diary (EPD), which will be provided to the parents/caregivers (as of Amd 1). Incremental recovery and trough levels of BAY 81-8973 will be assessed in all subjects. Suitable subjects will be given the opportunity to participate in the pharmacokinetic (PK) evaluation (as of Amd 3). Participation is optional, and requires consent. PK parameters (maximum concentration [Cmax], half-life, area under curve [AUC], Mean Residence Time [MRT] and clearance) may be assessed using a sparse sampling schedule. In the event that any subject acquires an inhibitor to FVIII, Immune Tolerance Induction (ITI) will be offered. The subject may receive BAY 81-8973 up to 200 IU/kg daily or 100 IU/kg twice a day for 18 months. Treatment will be at the discretion of the treating physician, although the detailed treatment plan should be agreed with the Coordinating Investigator (as of Amd 7). Subject commences on ITI therapy will be followed up within the extension study. Data on treatment, FVIII measurements, and inhibitor levels will be collected. (as of Amds 1 and 6)

4. General Statistical Considerations

4.1 General Principles

The statistical evaluation will be performed by using the software package SAS release 9.2 or higher (SAS Institute Inc., Cary, NC, USA).

All data (efficacy, safety and demographic data) will be listed and study summary tables will be provided where appropriate. Variables measured on metrical scales will be summarized using descriptive statistics that will include: the number of non-missing observations, the arithmetic mean, the sample standard deviation, the median, the minimum and maximum, as well as the first and third quartiles where appropriate. Frequency tables will be provided for variables measured on ordinal or nominal scales. Tables will display the number and percentage of subjects falling within a particular category.

Data will be displayed for efficacy and main parts of demography by

- type of subjects: PUPs; MTPs; total
- inhibitor status: Subjects without inhibitor; Subjects with low titer inhibitor; Subjects without inhibitor or with low titer inhibitor; Subjects with high titer inhibitor
- ➢ inhibitor status of PUPs: The same as above restricted to PUPs

For safety data will be displayed for type of subject (PUPs; MTPs; total) only.

In general, data will be displayed as measured, individual values will be presented in listings.

4.2 Handling of Dropouts

In this study, all efforts must be taken to engage patients to comply with all study procedures and to continue to be followed until the end of the study.

A subject who discontinues study participation prematurely for any reason is defined as a "dropout" if the subject has received at least one dose of study drug. At the time of discontinuation, subjects should be requested to have a final visit to have performed the procedures and evaluations scheduled for the final study visit as described for last visit. Subjects who are withdrawn after the start of treatment will not be replaced.

A subject is regarded a "screening failure" if he terminates the study for any reason (e.g., failure to satisfy the selection criteria) prior to the time point used for the definition of "dropout".

In all cases, the reason for withdrawal must be recorded in the electronic case report form (eCRF) and in the subject's medical records.

The number of subjects who prematurely discontinue the study during the treatment phase or during the post-treatment observation phase for any reason, as well as the reasons for premature discontinuation of study, will be displayed.

Subjects who prematurely withdraw prophylaxis treatment due to inhibitor development will be considered premature discontinuations from Part B, even though they may continue with ITI treatment in the extension phase. For this reason a separate tabulation of the reason for premature termination will be given, where all reasons connected to ITI or inhibitors will be combined to "INHIBITOR MANAGEMENT". In addition subjects, who prematurely

discontinued part B without a clinical reason (inhibitor, AE) or withdrawal of informed consent or protocol violation, but just for logistical problems to match exactly the 50 EDs, will be counted as completers in this table.

Subjects can be withdrawn at their parent's request, or at the investigator's discretion due to, for example, development of inhibitory antibody or lack of compliance. The reasons for withdrawal will be listed. The annualized number of total bleeds will be calculated for these withdrawn subjects, and the time of the last procedure in a visit or the last infusion in the EPD will serve as the end time point used for calculation.

4.3 Handling of Missing Data

All missing or partial data will be presented in the subject data listing as they are recorded on the Case Report Form (CRF).

General rules

When appropriate, the following rules will be implemented so as not to exclude subjects from statistical analyses due to missing or incomplete data:

• Efficacy Variables

The EPD is designed to allow the collection of date and time for each infusion or bleed as well all other relevant data. Each subject's bleeding period start date will be needed to allocate the bleedings to the respective period. If dates for bleeds and infusions of rescue medication are both missing then these bleeds cannot be counted. If the bleed date is missing, but the infusion date is available, infusion date will be used.

If the details of a bleed are missing (e.g., type of bleed spontaneous, nonspontaneous/non-traumatic or traumatic), the bleed will be counted for all categories of bleeds, but not for the corresponding subgroup of bleeds.

• AE Variables

For the purpose of treatment-emergent flags, missing AE start day will be imputed as the 15th of the month. However, if the AE start day is missing, but the AE starts during the same month or on the same day as the first dose, but the AE start time is missing, the AE start day (and time in the second case) will be taken from first dose start day (and time). If both day and month of AE start date are missing, day and month will be imputed as the date of the first dose. Imputation date is to be set not to be before date of birth (if available).

Drug-related AE tables will also include AEs with missing values of causality. Missing end date for an AE will not be imputed.

• Missing or incomplete concomitant medication start and end date

When computing concomitant medication start dates, if day is missing, use 15. If month and day are missing, use 1 JUL. If necessary, adjust imputed dates so they are not before the birth date. A totally missing start date will not be imputed.
Missing end date for a concomitant medication will not be imputed.

• Additional descriptive analyses in the presence of missing data

The number of subjects who prematurely discontinue the study (subjects who stop updating the EPD and stop coming back for scheduled visits) and study treatment (subjects who stop using the medication but still come back for the last visit) for any

Statistical Analysis Plan PH-41074

Protocol No.: BAY 81-8973 / 13400

reason, as well as the time point and reasons for discontinuation of study and study treatment, will be reported. All dropouts will be evaluated with respect to the reasons for discontinuation of study and/or study treatment and potential dropout patterns When computing age at diagnosis, age at start of therapy, age at start of prophylaxis, and time since start of therapy; if day is missing, use 15. If month and day are missing, use 1 JUL. If necessary, adjust imputed dates so they are not before the birth date. A totally missing date will not be imputed.

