4.3 Handling of Missing Data

Each subject's start and stop date will be needed to compute the annualized bleeding rate. If a bleed date is missing, but an infusion date is available, infusion date will be used as the bleed date. Otherwise, use imputation rules as specified in "Analysis Datasets" document.

Missing or incomplete AE start and end date or time: For the purpose of treatment emergent flags, missing AE start day will be imputed as the 15th of the month. However, if the AE start day is missing, but the AE starts during the same month as the first dose, or if the AE starts on the same day as the first dose, but the AE start time is missing, the AE start day (and time in the

second case) will be taken from first dose start day (and time). If both day and month of AE start date are missing, day and month will be imputed as July 1st, or the date of the first dose, whichever comes later.

Drug-related AE tables will include AEs with missing values of causality.

Imputation rules for AE durations (days) are described in the analysis datasets specifications.

When computing age at diagnosis, age at start of therapy, and time since start of therapy; if day is missing, use 15. If month and day are missing, use July 1. If necessary, adjust imputed dates so they are not before the birth date.

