6.4 Safety

All subjects receiving any amount of study drug will be included in the safety analysis. Laboratory findings, adverse events, concomitant medications, and medical history data will be provided in subject listings.

Laboratory values, incidence of high or low abnormal values, changes from baseline (Baseline value is the last value before the first study drug infusion.) will be summarized. Vital signs will be summarized. Individual listings of AEs [including AEs as reported, start, duration, severity, relation to study drug] will be provided. The incidence of treatment-emergent AEs will be summarized using the Medical Dictionary for Regulatory Affairs (MedDRA). AEs with a start date prior to first infusion or more than 3 days after the last infusion are not treatment emergent. Treatment emergent determination will be derived after missing or incomplete AE start date is imputed. Imputation rules for missing and incomplete AE start are described in Section 4.3

Two laboratory analytes, Anti HSP70 and Anti BHK, will be summarized in a listing that will include all values for those subjects with any positive result. Incidence of HSP-70 antibody formation and hamster protein antibody formation will be assessed from these laboratory tests.

Inhibitor development, as measured by Bethesda assay, as well as the results from all ELISA assays, will be summarized by preparation and timepoint and presented in subject listings. The frequency of subjects who develop positive inhibitor titers (Bethesda ≥ 0.6 BU) will be presented.

Vital signs and change from baseline of vital signs will be summarized with descriptive statistics distinguishing pre-infusion and post-infusion readings. Baseline is the last measurement before the first study drug infusion. Post-infusion minus pre-infusion values will be summarized at Month 1, Month 2, and final visit in the main study.

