6.4.1 Adverse events

The investigator has to record on the respective CRF pages all adverse events occurring in the period between the signing of the informed consent form and the end of the follow-up phase. The original terms used by investigators to report AEs via the CRFs will be coded using the Medical Dictionary for Regulatory Activities (MedDRA).

For each AE, the number and percentage of subjects who experienced at least 1 occurrence of the given event will be tabulated according to the affected primary system organ class (SOC) and preferred term (PT) by dose cohort and dose actually received. A total column will be included in all safety summaries.

Frequency tables, showing an overall summary of number of subjects with drug-related AEs, SAEs and AESIs will be given, and will include the following information:

- maximum intensity for any AE,
- AE related deaths,
- AE resulting in permanent discontinuation of study drug,
- treatment emergent AE.

AEs will be considered treatment-emergent if they begin after the first administration of study drug and they do not start after more than 7 days after the last administration. Determination of whether or not an event is treatment-emergent will be derived after the missing or incomplete AE start date is imputed. In case an adverse event starts on the day of first administration of study drug and the time of onset is not known, the event is considered to be not treatment emergent, if it is reported to occur before the first dose of study drug. In all other cases the event is considered to be treatment emergent. Inhibitors will be defined as treatment-emergent if they develop after first study drug application. Imputation rules for missing and incomplete AE start are described in section 4.3.

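### Treatment emergence is judged on an imputed mid-month start date with no protection at the last dose, so a partly dated adverse event that may have begun on treatment can be flagged as not treatment-emergent

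*SAP*

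**What the plan says.** **Imputation.** Section 4.3 of each SAP states, for the purpose of treatment-emergent flags, that a "missing AE start day will be imputed as the 15th of the month". Where the event falls in the first-dose month, "the AE start day (and time in the second case) will be taken from first dose start day (and time").

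The SAPs differ when only the year is known. In Part A, "day and month will be imputed as July 1st, or the date of the first dose, whichever comes later". In Part B, "day and month will be imputed as the date of the first dose"; the 1 July rule there covers concomitant medication and history dates, not adverse events.

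**Window.** In Part B (6.4.1) events count if "they do not start after more than 7 days after the last administration". In Part A (6.4) events starting "more than 3 days after the last infusion are not treatment emergent".

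**Order.** Part B 6.4.1: "Determination of whether or not an event is treatment-emergent will be derived after the missing or incomplete AE start date is imputed". Part A 6.4 has the same order.

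**Exception.** Part B 6.4.1 adds: "Inhibitors will be defined as treatment-emergent if they develop after first study drug application". The Part A SAP has no such sentence.

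**The concern.** The rule treats the two ends of treatment differently. At the first dose, doubt about the day is resolved towards counting the event. At the last dose there is no matching provision, so a day that nobody recorded decides whether the event stays in. An event recorded only by month can be classed as not treatment-emergent although the record is fully compatible with onset on treatment or inside the post-dose window.

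Safety is part of the primary objective, and the events exposed lie around stopping. Both SAPs otherwise lean the cautious way: missing causality counts as drug-related, and first-dose-month events count as emergent. Part B 4.3 also says its rules are meant to avoid exclusions caused by incomplete data. This gap works against that aim.

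**Working it through.** The plan states no figure on this point, so the check applies its date rules directly.

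**Inputs.** Imputed day 15 (4.3, both SAPs); window of 7 days (Part B 6.4.1) or 3 days (Part A 6.4); flag set after imputation. **Assumptions.** Last-dose dates are spread evenly over a 365-day year, and the event is not in the first-dose month.

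**1. Event dated only to the last-dose month.** With last dose on day d and window w, the event is flagged out if 15 > d + w.
- Part B, w = 7: d = 1 to 7. Share of last-dose dates: 7/30.44 = 23%.
- Part A, w = 3: d = 1 to 11. Share: 11/30.44 = 36%.

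Examples:

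| Part | Last dose | Event recorded as | Imputed | Window ends | Flag |
|---|---|---|---|---|---|
| B | 5 March | March | 15 March | 12 March | out |
| B | 8 March | March | 15 March | 15 March | in |
| A | 11 November | November | 15 November | 14 November | out |
| A | 12 November | November | 15 November | 15 November | in |

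In the first row, any true onset from 1 to 12 March would have been treatment-emergent.

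**2. How many of those events are wrongly dropped.** The shares in step 1 include events that really began after the window. Add uniform onset over the month: for each affected d, the in-window onset days number d + w.
- Part B: sum of (d + 7) for d = 1 to 7 is 28 + 49 = 77. 77/30.44² = 8.3%.
- Part A: sum of (d + 3) for d = 1 to 11 is 66 + 33 = 99. 99/30.44² = 10.7%.

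Day-by-day enumeration of the year also gives 8.3% and 10.7%.

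**3. The opposite error.** When the last dose is on day 8 or later (Part B) or day 12 or later (Part A), the 15th lies inside the window, so late-month events after the window are counted. The same enumeration gives 13.7% of last-dose-month events in each part.

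**4. Event dated only to the following month.** If the window runs into the next month but ends before its 15th, the event is flagged out although onset on the first days of that month would be in the window. Part B example: last dose 28 March, window to 4 April, event recorded as April, imputed 15 April. This applies to 84 of 365 last-dose dates (23%) in Part B and 36 of 365 (10%) in Part A. With step 1 (84 and 132 dates), 168 of 365 last-dose dates (46%) are exposed in each part.

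**5. Part A, only the year known.** If the first dose was before 1 July of that year, the event goes to 1 July and is flagged out when the last infusion was on or before 27 June: 178/365 = 49% of last-dose dates. This too is a share of dates, not of events wrongly dropped.

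**The case against.** Four points on the other side have force.

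- **The error runs both ways.** A reader might infer that the rule always under-reports. Step 3 shows that it does not: under uniform onset over the whole month, more events are wrongly kept than wrongly dropped. The balance also depends on how long after the last dose events are collected; the protocol's follow-up call is 1-2 weeks after treatment ends. The errors are not equivalent, though: wrongly kept events are conservative for safety, and wrongly dropped ones are not.
- **The large percentages are not losses.** A reader might take 23%, 36% or 49% as the fraction of events lost. They are shares of last-dose dates. For last-dose-month events the wrongly dropped fractions are about 8% and 11%.
- **Safeguards exist.** Part B inhibitors count whenever they develop after first dose, so the documents do not support a claim that Part B inhibitors are lost. Adverse events are listed individually in both parts, and Part B listings show partial dates as recorded. Part B 6.4.1 does not expressly limit its system organ class table to treatment-emergent events. The protocol requires start and stop dates and weekly contact in the main study, so partial dates should be few. Children still dosed in the extension are largely unaffected, unless last administration is read as the last Part B dose, which the SAP does not say.
- **Part A is reported.** The Part B SAP says the 6-month Part A analysis is complete, so a new sentence cannot alter it.

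All four limit the size and reach of the point. None supplies the missing provision at the last-dose end.

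**Conclusion.** The gap is real and minor. As written, both SAPs can flag a partly dated event as not treatment-emergent when its recorded date is compatible with onset on treatment or within the window. The percentages rest on evenly spread last-dose dates and, for the 8% and 11%, on onset uniform over the month. They apply only to events dated to the last-dose month in children whose dosing has ended, outside the first-dose month. The documents do not say how many events have partial dates, so no absolute count can be given; it is likely small. In Part B the point concerns events other than inhibitors.

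**What to change.** Add one sentence to section 4.3 of the Part B SAP, and carry it into any remaining or final analysis of Part A and extension data:

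*An adverse event with a partial start date is classed as treatment-emergent unless the known part of that date, or a known end date before the first dose, rules out onset between the first dose and the end of the treatment-emergent window.*

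The flag should rest on this rule, not on the imputed day. Do not simply cap the imputed date at the last dose: with a last dose on 28 March and an event recorded as April, the cap would contradict the recorded month. If a date is still needed for other purposes, keep it within the recorded month or year.

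The cost is one sentence and a small programming change. The downside is that a few truly post-window events may be counted as treatment-emergent.
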